2.1.2 In Range (IR) Population

The aim of the IR population is to include the patients that have reached the targeted phosphate levels for the trial. Table 1 in section 4.4.1 below presents the "in range" phosphate range for each treatment arm. Phosphate levels will be measured on a monthly basis for each patient in the trial. Patients that are in range for 75% of their monthly phosphate measures will be included in the IR population.

2.1.3 In Range 2 (IR2) Population

The IR2 population will be defined similarly to the IR population, except it will include patients that are in range for 50% of their monthly phosphate measures.

2.2 **Protocol Deviations**

Because this is a pragmatic trial intended to evaluate effectiveness of the phosphate targets under real-world conditions, protocol deviations will be limited to: 1) enrollment of individuals who do not meet eligibility criteria or provide informed consent, and 2) breaches of participant confidentiality. Deviations will be reported by the DCRI to the IRB.

3. STUDY ENDPOINTS

3.1 Primary Endpoint

The primary outcome for HiLo is the hierarchical composite of: 1) time to all cause death followed by 2) number of all cause hospitalizations. The use of this endpoint will allow for simultaneous testing of both mortality and hospitalizations while prioritizing mortality as the more important health outcome to consider. Time zero for the time to all cause death portion of the endpoint will be the date of the first dialysis session after the patient has consented to participate in HiLo.

3.2 Secondary Endpoints

Time to all cause death and PPY hospitalization rates will be investigated separately as secondary endpoints. The patient level PPY hospitalization rate will be calculated by dividing the patient's number of hospitalizations during the follow-up period by the total length of the patient's follow-up time in years.

Other secondary outcomes will be the change from baseline in the following clinical measures: serum albumin and PCR. The baseline measure for these will be the latest available measure before consent.

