## 4.3.2 Participant Eligibility

The eligibility criteria are broad in order to maximize the generalizability of the trial findings.

- Inclusion criterion:
  - Adults ≥18 years
  - Undergoing 3 times weekly in-center hemodialysis and having received dialysis treatment for at least 3 months
  - Able to provide informed consent
- Exclusion criteria:
  - Females who are pregnant or who plan to become pregnant while in the study
  - Calciphylaxis
  - o Nocturnal in-center dialysis

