#### Laboratory data: monthly

In alignment with usual practice, all values available for the following laboratory test results will be made available to the DCRI by electronic data transfer on a monthly basis.

- Hemoglobin
- Albumin
- Calcium
- Phosphate
- Protein catabolic rate
- Serum ferritin
- Transferrin saturation

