4.5.2 Analyses of the Secondary Endpoints

The hypothesis of the main secondary endpoint of time to all-cause death will be tested in the ITT population using a Cox Proportional Hazards model including phosphate target group as an explanatory factor. The hazard ratio and 95% CI for the high phosphate target versus the low phosphate target will be calculated from the estimated model parameters. If the confidence interval does not include 1, then the null hypothesis will be rejected.

The all-cause PPY hospitalization rates will be analyzed under the following hypotheses:

H₀:
$$\mu_H = \mu_L vs. H_1: \mu_H \neq \mu_L$$

Where μ_H and μ_L are the all-cause PPY hospitalization rates in the Hi and Lo treatment arms respectively. A two-sided 95% confidence interval for the difference in the cause-specific PPY hospitalization rates between the study arms will be estimated under normality assumptions. If confidence interval does not include 0, then the null hypothesis will be rejected.

For the continuous longitudinal outcomes (change from baseline in serum albumin and PCR), mixed effect models will be created to test the null hypothesis that the change of each measure

will not differ by treatment group. The phosphate target group and the baseline measure will be included as fixed effect covariates and study site will be included as a random effect covariate in the model.

Two covariance structures for this model will be considered: the compound symmetry structure (CS) and the auto-regressive(1) (AR1) structure. Each covariance structure will be compared using the Akaike information criterion (AIC) and the Bayesian information criterion (BIC). The structure that provides better results on the AIC and the BIC will be chosen for the final adjustment model.

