4.6.2 Clinical Safety Laboratory Events

Laboratory measurements are collected either monthly or quarterly for all patients as part of routine clinical care. Predetermined laboratory safety events will be collected. Below are defined the laboratory events of interest in HiLo:

- Hypophosphatemia, defined as serum phosphate <2.0 mg/dL
- Hyperphosphatemia, defined as serum phosphate >7.5 mg/dL
- Hypercalcemia, defined as total uncorrected serum calcium >10.5 mg/dL
- Excessive iron supplementation, defined as serum ferritin >1000 ng/mL and transferrin saturation (TSAT) >50%
- Secondary hyperparathyroidism, defined as parathyroid hormone (PTH) levels greater than 9 times the upper limit of normal for the assay

A listing of laboratory safety events will be created, along with a table of counts of each type of event by treatment group.

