5. CONVENTIONS

5.1 **Baseline Measurements**

Unless specified otherwise, a baseline value is the last assessment taken prior to the first dialysis session after consent. When there is a missing baseline assessment, it will not be imputed, thus, patients will be excluded from any changes from baseline analysis for which they have a missing baseline value.

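### Albumin and PCR are adjusted for one last pre-consent value; adding earlier monthly values, where on file, may narrow the treatment-effect interval

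*SAP*

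**What the plan says.** SAP 3.2 defines baseline albumin and PCR as a single value: "The baseline measure for these will be the latest available measure before consent". The general convention in SAP 5.1 also takes one value, with a slightly different anchor: "a baseline value is the last assessment taken prior to the first dialysis session after consent". It applies unless something else is specified, so 3.2 governs here.

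SAP 4.5.2 models change from baseline in a mixed model with site as a random effect. "The phosphate target group and the baseline measure will be included as fixed effect covariates". The covariance is chosen by AIC and BIC between "the compound symmetry structure (CS) and the auto-regressive(1) (AR1) structure". SAP 4.5.3 repeats these models with six further covariates.

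On what may be on file, Protocol 4.3.2 requires "having received dialysis treatment for at least 3 months". Protocol 5.4 lists albumin and PCR among the monthly laboratory data and says "all values available for the following laboratory test results will be made available to the DCRI by electronic data transfer on a monthly basis". Neither document uses a value before the last one, and neither gives a pre-consent look-back for the extract.

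On missing baselines, SAP 5.1 says "patients will be excluded from any changes from baseline analysis for which they have a missing baseline value", and SAP 5.3 rules out imputation other than of dates.

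**The concern.** One routine monthly value carries all of its month-to-month noise. If patients differ persistently in albumin and PCR, the last value together with earlier ones predicts a patient's later level better than the last value alone. A baseline covariate that predicts better leaves less residual variance and a narrower interval for the arm effect.

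Higher albumin and higher PCR in the less stringent arm are named secondary hypotheses (Protocol 2.1, SAP 1.1). At stake is the width of their intervals. The earlier values would come from the provider records that already supply the baseline, so the improvement would need no new test or visit.

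**Working it through.** **No plan figure to reproduce.** The documents give no SD, effect size, power or within-patient correlation for albumin or PCR. The stated power above 95% is for the hierarchical primary endpoint and does not depend on this baseline.

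**Inputs from the documents.** Baseline is a fixed covariate and CS and AR(1) are the candidate structures (SAP 4.5.2). Values are monthly (Protocol 5.4). There are about 1,900 patients per arm (Protocol 5.3), and alpha is 0.05 two-sided (SAP 4.1).

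**Assumptions.** Unit variance, two earlier monthly values besides the last one, m = 24 complete monthly follow-up values, no site effect, and the correlations in the table.

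**Formula.** The variance of the arm effect is proportional to the residual variance V of a patient's follow-up mean given the baseline covariates:

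V = a'Fa − (a'C) B⁻¹ (C'a)

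Here F is the covariance of the follow-up values, B that of the baseline covariates, C the cross-covariance, and a averages over the m values. Under CS with k baseline values this becomes

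V = [1 + (m−1)ρ]/m − kρ²/[1 + (k−1)ρ].

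For ρ = 0.5 and m = 24, the first term is 12.5/24 = 0.5208. With k = 1, V = 0.5208 − 0.25 = 0.2708. With k = 3, V = 0.5208 − 0.75/2 = 0.1458. The ratio is 0.54.

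| Assumed pattern | V, last value only | V, last value plus mean of two earlier | Ratio |
|---|---|---|---|
| CS, ρ = 0.3 | 0.2392 | 0.1604 | 0.67 |
| CS, ρ = 0.5 | 0.2708 | 0.1458 | 0.54 |
| CS, ρ = 0.7 | 0.2225 | 0.1000 | 0.45 |
| Stable share 0.3, AR 0.3 | 0.2550 | 0.2062 | 0.81 |
| Stable share 0.7, AR 0.3 | 0.2250 | 0.1388 | 0.62 |
| Stable share 0.3, AR 0.5 | 0.2743 | 0.2432 | 0.89 |
| Stable share 0.7, AR 0.5 | 0.2278 | 0.1680 | 0.74 |
| Stable share 0.3, AR 0.8 | 0.3410 | 0.3325 | 0.975 |
| Stable share 0.5, AR 0.8 | 0.3131 | 0.2969 | 0.948 |
| Pure AR(1), 0.7 | 0.1997 | 0.1997 | 1.00 |

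Pure AR(1) at 0.5 and 0.9 also gives 1.00. A simulation of the baseline-adjusted analysis under CS (ρ = 0.6, m = 27) gave a ratio of 0.49, against 0.486 from the formula.

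**Fewer follow-up values.** With m = 1 under CS, the ratio is 0.83125/0.91 = 0.91 at ρ = 0.3 and 0.3875/0.51 = 0.76 at ρ = 0.7, a fall of 9-24%. With a stable share of 0.3-0.7 and autocorrelation 0.5 it is 1-6%.

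**Only one earlier value.** With m = 24, the fall is 20-39% under CS (ρ = 0.3-0.7), and 6-25% with a stable share of 0.3-0.7 and autocorrelation 0.3-0.5.

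**Replacing the last value by a plain mean of three.** Under pure AR(1) with m = 27 this raises the variance by 0.6-2.8% (autocorrelation 0.5-0.9). The last value should therefore stay in the model.

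**Absolute size.** The detectable difference at 80% power is (1.960 + 0.842) × √(2V/1900). Under CS with m = 24 it is 0.043-0.047 SD with the last value alone and 0.029-0.036 SD with the second covariate, a reduction of 0.008-0.014 SD. With autocorrelation 0.8 (stable share 0.3-0.5) the reduction is about 0.001 SD.

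**The case against.** A single last value used as a covariate is a legitimate choice and matches the SAP's general convention. Three stronger readings might be inferred, and the documents support none of them.

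- **That at least three pre-consent values exist for everyone.** The 3 months on dialysis need not have been at a participating provider. A patient just past 3 months, or recently transferred in, may have only one or two values on file. SAP 4.6.2 also describes routine laboratory frequency loosely ("Laboratory measurements are collected either monthly or quarterly for all patients as part of routine clinical care"), although Protocol 5.4 puts albumin and PCR in the monthly group and only parathyroid hormone in the three-monthly one.
- **That the interval is certainly too wide.** Under pure AR(1), one of the SAP's own candidates, the last value already carries all the baseline information. Nothing in the documents settles which pattern applies.
- **That the estimates are biased or the endpoints short of power.** Arms are randomized and baseline is already adjusted for, so no bias follows. With the last value alone, differences of about 0.05 SD or less are already detectable in most of the patterns tested, and the plan sets no target for these endpoints.

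The large percentages also assume 24 complete values. If the planning rates in Protocol 8.1 (15% annual mortality, 5% annual loss) compound independently, about 0.85² × 0.95² = 65% of the standard-of-care arm is still followed at 24 months. Many patients therefore contribute fewer values and gain less. The site effect and the adjustment covariates of SAP 4.5.3, which the calculation omits, may absorb part of the stable between-patient variance.

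Finally, a second covariate is undefined for a patient with only one value. Given SAP 5.1 and 5.3, such patients could drop out of the model, and where the gain is 3-5%, losing a similar share of patients would cancel it.

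All of this stands as a limit on the claim. It does not remove the point: in the patterns tested, keeping the last value and adding a second covariate gains or breaks even, provided that nobody is dropped.

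**Conclusion.** The point holds as an optional, low-cost gain in precision on two secondary endpoints. The plan uses one baseline value, earlier monthly values are likely on file for most patients, and those values are not used.

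Under the stated assumptions the variance of the arm effect falls by 33-55% under compound symmetry, by 11-38% with a stable patient level plus autocorrelation 0.3-0.5, by about 3-5% with autocorrelation 0.8 and a stable share of 0.3-0.5, and by nothing under pure AR(1). Under compound symmetry the interval is 18-33% narrower (square roots of the variance ratios: 0.82 to 0.67). All the correlations are assumptions, and incomplete follow-up or fewer earlier values reduces the gain. The primary endpoint is unaffected.

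**What to change.** In SAP 3.2, 4.5.2 and 4.5.3:

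- Keep the last pre-consent value, both as the baseline for change and as a covariate.
- Add the mean of any other values in the 90 days before consent as a second baseline covariate, separately for albumin and PCR.
- State that a patient with no earlier value in that window is kept by setting the second covariate equal to the last value, with a no-earlier-value indicator if wanted. Make this an explicit exception to SAP 5.3, so that nobody is excluded for this reason.
- State the 90-day look-back in the data extract specification.
- Fix the rule before results by arm are seen.

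The cost is SAP wording, a slightly longer extract and one or two extra model parameters among about 3,800 patients. No visit, test or treatment changes. If the providers cannot supply the earlier values, the current definition can stand.

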3.3 Additional Endpoints

The percent of hospitalization days during the follow-up period will be investigated as an additional endpoint. At the individual patient level, this endpoint will be calculated as the total number of days spent in the hospital divided by the total number of days of follow-up for that patient.

If data are available, an endpoint filtering out COVID-19 related death and hospitalizations will be created. This endpoint will be identical to the primary endpoint, however, deaths and hospitalizations that are attributed to COVID-19 will not be counted as events as they would be in the primary endpoint.

4. ANALYSIS METHODS

4.1 General Principles

This analysis plan is intended to support the primary and main secondary manuscripts planned for the HiLo study. Analysis plans for other manuscripts will be provided in separate documents.

In addition to specific analyses and presentations that are detailed in the following sections, results will be summarized for continuous measures using descriptive statistics, including the number of patients, mean, standard deviation, median and range as appropriate. For categorical variables, counts and percentage per treatment group will be presented. Unless otherwise specified, all statistical tests will have a two-sided significance level of α =0.05.

4.1.1 Control of Type I Error

To account for repeated significance testing of the accumulating data, the group sequential method of Lan and DeMets will be used as a guide for interpreting interim analyses. Monitoring boundaries for the primary endpoint will be based on a two-sided symmetric O'Brien-Fleming type spending function with an overall two-sided significance level of α =0.05. The O'Brien-Fleming approach requires large critical values early in the study but relaxes (i.e., decreases) the critical value as the trial progresses. A single planned interim analysis using alpha spending will be targeted to occur after the first 2000 to 2400 subjects have been enrolled with at least 24 months of median follow up time accrued. Additional interim analyses are not currently planned but may be performed upon request by the Data Safety and Monitoring Board (DSMB).

Assuming that the interim analyses take place as currently planned with just a single analysis after ~50% of subjects have been enrolled with at least 24 months of median follow up time accrued, the critical p-value for the test of the null hypothesis of no difference at the first interim analysis will be 0.001 and a result of |z| <3 or p>0.001 would suggest that the trial should continue. In order to maintain the overall 5% significance level of the trial, the critical p-value for declaring there to be a significant difference in the primary endpoint at the final analysis will be decreased from 0.05 to 0.049. However, the critical p-values for the interim analysis can be adjusted appropriately if additional interim analyses are requested by the DSMB.

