1.3 Number of Patients

Sample size calculations

A simulation was performed in order to determine whether a sample size of 3800 provides sufficient power to reject the null hypothesis of no difference between the treatment arms in time to all cause death and number of hospitalizations.

The simulation population was created under the following parameters:

- 1:1 randomization
- For each participant, administrative censoring occurs uniformly randomly between 2 to 4 years
- Annual loss to follow up rate of 5% (for example, due to kidney transplantation, change in dialysis modality, withdrawal due to participant choice, etc.)
- Annual mortality rate of 15% in the Lo treatment arm vs. 12.8% in the Hi treatment arm.
- An average of 35% of the study population are not susceptible to hospitalization and have no chance of experiencing a hospitalization during the course of the study (zero-inflated distribution of hospitalization)
- The remaining susceptible population experiences an average a 2 hospitalizations per year in the Lo treatment arm vs. an average of 1.89 in the Hi treatment arm.

The above population was simulated across 1000 iterations. The simulated population and outcomes were analyzed using the methods described in protocol section 4.5.1. Power was estimated as the number of iterations with a p-value less than 0.05 divided by the total number of iterations.

The estimated power from the simulation indicate that a sample size of 3800 patients will have more than 95% power.

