Here, p is the number of participants in the treatment arm. The value of T/V^{1/2} will be compared to the standard normal distribution to determine the test p-value. A p-value of less than 0.05 will indicate that there is a difference between the treatment groups.

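### SAP 4.1.1 gives one interim boundary as two different cut-offs (p = 0.001 and |z| = 3), and SAP 4.5.1 tests the primary endpoint at 0.05 where 4.1.1 sets 0.049

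*SAP*

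**What the plan says.** SAP 4.1.1 adopts the Lan-DeMets method with a two-sided symmetric O'Brien-Fleming-type spending function and overall alpha 0.05. The boundary is advisory: it "will be used as a guide for interpreting interim analyses". One interim look is planned, "after the first 2000 to 2400 subjects have been enrolled" and with at least 24 months of median follow-up. The same section later describes this as about 50% enrolled. No information fraction is given.

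Three thresholds follow in 4.1.1:

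- Interim: "the critical p-value for the test of the null hypothesis of no difference at the first interim analysis will be 0.001".
- Interim, restated: "a result of |z| <3 or p>0.001 would suggest that the trial should continue".
- Final: the critical p-value for the primary endpoint "will be decreased from 0.05 to 0.049".

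SAP 4.5.1, which defines the Finkelstein-Schoenfeld test for the same endpoint, ends with: "A p-value of less than 0.05 will indicate that there is a difference between the treatment groups". It does not refer to 4.1.1. SAP 4.1 supplies the default: "Unless otherwise specified, all statistical tests will have a two-sided significance level of" 0.05.

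Protocol 8.5.1 says that the interim look assesses efficacy on the primary outcome. Protocol 9.2 pre-specifies no stopping rule for efficacy or futility. SAP 4.7 leaves the details to a separate interim analysis plan.

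**The concern.** There are three faults, in descending order of certainty.

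1. The two interim cut-offs are offered as one boundary but are not equivalent on a two-sided scale. A monitoring board holding an interim |z| of, say, 3.1 finds it beyond one figure and short of the other.
2. The primary endpoint has two final significance levels. A final p of 0.0495 is a positive trial under 4.5.1 and a negative one under 4.1.1.
3. The interim 0.001 does not look like the output of the named spending function at about half the information, although the final 0.049 does.

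The stake is not a material loss of type I error control. It is that the threshold for the main claim, and the guidance given to the board, should each be a single number fixed in advance.

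**Working it through.** **Inputs.** From SAP 4.1.1: overall two-sided alpha 0.05, O'Brien-Fleming-type spending, interim p = 0.001, |z| = 3, final 0.049. From SAP 4.5.1: final 0.05 and a standard normal reference. From SAP 1.3: "a sample size of 3800 patients will have more than 95% power". The information fraction t is an assumption throughout. A ratio of head-counts is not an information fraction for a hierarchical rank test and is used only to set a range.

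**Step 1: convert the printed cut-offs (no assumption needed).**
- Two-sided p at |z| = 3: 2(1 − Φ(3)) = 0.0027.
- |z| at two-sided p = 0.001: Φ⁻¹(1 − 0.0005) = 3.29.
- Rounding does not close the gap. A one-sided p at z = 3 is 0.00135, which would come close to 0.001, but the SAP specifies a two-sided boundary.

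**Step 2: reproduce the SAP's pair from its spending function.** The alpha spent per side at the interim is α₁(t) = 2[1 − Φ(2.2414/√t)], with 2.2414 = Φ⁻¹(1 − 0.0125). The final critical value c solves P(|Z₁| ≥ z₁ or |Z₂| ≥ c) = 0.05, with correlation √t between Z₁ and Z₂.

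At t = 0.5, 2.2414/√0.5 = 3.170. This gives a two-sided interim p of 0.00305, z₁ = 2.963 and a final level of 0.0490. The SAP's 0.049 is reproduced and its |z| of 3 is close. Its 0.001 is not reproduced.

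| Assumed t | Basis | Interim z | Interim p | Final level |
|---|---|---|---|---|
| 0.4147 | solved for p = 0.001 | 3.290 | 0.0010 | 0.0497 |
| 0.4545 | 2000/4400 | 3.126 | 0.0018 | 0.0494 |
| 0.5 | half | 2.963 | 0.0031 | 0.0490 |
| 0.5455 | 2400/4400 | 2.819 | 0.0048 | 0.0485 |
| 0.6316 | 2400/3800 | 2.590 | 0.0096 | 0.0470 |

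An interim p that rounds to 0.001 needs t < 0.4422. A final level that rounds to 0.049 needs t > 0.4418. The printed pair is therefore consistent only near 44.2%, and only after rounding to three decimals.

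**Step 3: overall two-sided alpha.**
- Printed pair 0.001/0.049: 0.0493 at t = 0.4545, 0.0492 at 0.5, 0.0491 at 0.6316. This is conservative.
- Final 0.05, t = 0.5: 0.0502 with interim p = 0.001, 0.0508 with |z| = 3, 0.0510 with the function's own 2.963.
- Final 0.05 with the function's own boundary at t = 0.6316: 0.0529.
- If p = 0.001 is a fixed interim cut-off, the final level that exhausts 0.05 is 0.0497 at t = 0.4545, 0.0498 at 0.5 and 0.0499 at 0.6316.

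**Step 4: how often it would matter.**
- Interim |z| between 3.00 and 3.29 under the null: 0.0027 − 0.0010 = 0.17%.
- The same at 95% power: drift 1.960 + 1.645 = 3.605, so the interim mean is 3.605√t. The probability is 9.0% at t = 0.4545, 9.7% at 0.5 and 11.1% at 0.6316. At 80% power and t = 0.5 it is 5.9%.
- Final p between 0.049 and 0.05: 0.09% at 95% power, 0.24% at 80% power.

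**The case against.** The best case for the SAP is as follows.

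- Read literally, the word joining the two conditions makes p > 0.001 govern, because every |z| from 3.00 to 3.29 has p above 0.001 and so points to continuing. The |z| figure is then a loose gloss. **This stands as a reading.** But it leaves the |z| condition with no function, and a boundary restated in z should be the same boundary.
- The information fraction is not stated, and a stricter interim cut-off than the function gives is permissible. **This stands.** The mismatch with the function depends on t, and the printed pair does not inflate alpha. However, if the roughly 3,800 individually randomized participants are the only denominator, the range becomes 2000/3800 = 52.6% to 2400/3800 = 63.2%, where 0.001 fits worse.
- The larger alpha values (0.0510 and 0.0529) use a recomputed boundary, not the printed 0.001. **This is correct.** For the printed interim figure the value at 50% is 0.0502.
- The 0.05 default yields to 4.1.1, which is the more specific text. **This stands in part.** Yet 4.5.1 does not merely inherit the default; it restates 0.05 for this very test without a cross-reference.
- The boundary is advisory, and the separate interim plan or the board's charter may settle it. **This bears on the interim cut-off only.** The final level in 4.1.1 is worded as a firm rule, and an interim plan would not by itself alter the 0.05 in 4.5.1.

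**Conclusion.** The concern holds. Two inconsistencies follow from the text alone: |z| = 3 and two-sided p = 0.001 are different cut-offs, and the final primary test has two levels, 0.049 and 0.05. The third element, that 0.001 does not come from the named function, rests on an assumed information fraction. It holds at 45.5% and above, and fails only in a narrow region near or below 44%.

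The size is small. With the printed interim p, a final test at 0.05 puts overall alpha about 0.0002 above nominal at 50% information, and the printed 0.001/0.049 pair is conservative. The 9% to 11% chance of an interim result in the unclear range assumes that the claimed 95% power is true, and it is a chance of unclear guidance, not of a wrong decision. This should be corrected because these are the decision thresholds of the trial, not because error control is at risk.

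**What to change.** In SAP 4.1.1, state one interim cut-off with matching z and p, by either route:

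- **(a)** Keep p = 0.001 as a fixed cut-off, correct |z| to 3.29, and give the final level that goes with it, about 0.0498 at 50% information. Keeping 0.049 is also valid, but conservative, and should be described so.
- **(b)** Define the information fraction for the rank test, derive both levels from the spending function, and recompute them at the fraction actually reached.

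In SAP 4.5.1, replace the fixed 0.05 with a reference to the final level in 4.1.1. Carry the same figures into the separate interim analysis plan. Reconcile the boundary's status with Protocol 9.2, for example by stating that it is non-binding guidance to the monitoring board.

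Route (a) is a change of wording. Route (b) also needs some statistical work to define information for the hierarchical test. Neither changes sample size, data or schedule. Testing at 0.049 instead of 0.05 costs about 0.1 percentage point of power at 95% power and 0.2 at 80%.
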